I. Study Design

Feedback from the initial focus groups (IRB application 01815) will be used to modify the therapist and patient materials prior to implementation of the B-FIT protocol. After materials are ready, therapists will receive a short, intensive training that will include didactic material and role-play rehearsal of each intervention. Following this training, six patients with alcohol use disorders (AUDs) and their concerned family members (CFMs) will be recruited to pilot test the treatment. A short debriefing questionnaire will be administered to the therapist, patient, and CFM after each session that will query several aspects of the session: (a) length and timing; (b) ease or difficulty in delivering or understanding material; (c) relevance to the patient and family member; and (d) open-ended comments about the intervention. Based on the experience with the first six patients and family members, additional adjustments will be made to the therapist manual and handouts. A second set of focus groups will be used to obtain feedback on the revised materials using the same procedures detailed in IRB application 01815. Adjustments to the materials will be completed in response to this feedback. These revised materials will then be used for a small clinical trial to evaluate the B-FIT intervention compared to treatment-as-usual (TAU).

II. Study Procedures

Table 1. Study Measures for Patients (PT) and Concerned Family Members (CFM)

PURPOSE	MEASURE	TYPE OF MEASURE	TIME TO ADMINISTER (MINUTES)	WHEN ADMINISTERED?							
				Screening		Baseline		Within-Treatment		Follow-Up	
PT	CFM	PT	CFM	PT	CFM	PT	CFM	PT	CFM	PT	CFM
Patient and Concerned Family Member measures											
Patient Eligibility	B-FIT Screening Interview - Patient. Includes:										
	• Important People Interview (importance item only)	Self-report	2	X							
	• AUDIT	Interview	10	X							
	• Drug Abuse Screening Test (DAST-10)	Interview	5	X							
	• SCID Psychotic screener	Interview	5	X							
	• Partner Violence Screen	Interview	2	X							

	SCID-Substance Abuse Module	Self-report	15	X							X
CFM Eligibility	B-FIT Screening Interview – Family. Includes:										
	• AUDIT	Interview	10	X							
	• Drug Abuse Screening Test (DAST-10)	Interview	5	X							
	• SCID Psychotic screener	Interview	5	X							
	• Partner Violence Screen	Interview	2	X							
Descriptive and Moderators	B-FIT Demographic Interview	Self-report	12		X	X					

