Initial screening. Patients will be screened in person or over the phone by study personnel. A simple checklist will be used to determine eligibility criteria related to date of treatment entry, age, and methadone maintenance status. AUD diagnosis will be assessed using the substance abuse module of the SCID interview (First et al., 2002). Psychotic symptoms will be assessed using the psychotic screening questions from the SCID (<http://www.scid4.org>). Presence of domestic violence will be assessed using the Partner Violence Screen (Feldhaus et al., 1997). These measures are all included in the B-FIT Screening interview. If eligible, the patient will be provided with a brief description of the study, will be asked to provide the name of an eligible CFM and verify frequency of contact and perceived importance (using one item from the Important People Interview, Longabaugh & Zywiak (1999), and will sign a release of information to allow study personnel to contact the family member and will be asked to mention study participation to the family member.

CFMs will be screened in person or over the phone by study personnel. A simple checklist will be used to assess family member age, frequency of contact with the patient, and current help-seeking status. Presence of domestic violence will be assessed using the Partner Violence Screen (Feldhaus et al., 1997). Psychotic symptoms will be assessed using the psychotic screening questions from the SCID (<http://www.scid4.org>). Severity of alcohol use will be assessed with the AUDIT (Saunders, Aasland, Babor, de la Fuente, & Grant, 1993); a score of 8 or greater will exclude the CFM from the study. Severity of drug dependence will be assessed with the DAST-10 (Skinner, 1982); a score of 3 or greater will exclude the CFM. If eligible, the family member will be provided with a brief description of the study, and asked about willingness to participate.

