Baseline assessment. Baseline assessments with patients and CFMs will be conducted by staff from the CASAA Program Evaluation Service (PES). Screening and baseline measures assess inclusion/exclusion criteria; locator and tracking information, sociodemographic descriptors, potential moderator variables; alcohol and other drug use, consequences, and diagnosis; CFM functioning and baseline measurement of hypothesized mediators of response to treatment (see Table 1). Each individual will be interviewed separately, and the patient and CFM may be scheduled at different or the same times for their baseline interviews. Patient baseline data collection will take approximately 2.5 hours; CFM baseline data collection will take approximately 1.25 hours. Patients will be compensated \$50; CFMs will be paid \$30.

Randomization. After the baseline interview, couples will be randomly assigned to TAU or TAU+B-FIT using urn randomization (Stout, Wirtz, Carbonari, & Del Boca, 1994) to balance groups on patient gender, severity of alcohol dependence, and type of CFM (parent versus partner versus other).

Treatment Conditions

Treatment as usual (TAU). Turquoise Lodge Hospital (TLH) provides detoxification services and residential treatment to adults with substance use disorders. The average residential stay is 18-21 days. TLH is currently developing an intensive outpatient program from which we also plan to recruit. **TAU at TLH consists of mainly group and some individual therapy.** Families do not typically participate in treatment but are allowed to visit patients during designated weekend hours.

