We believe the risks in this research are minimal. We foresee no physical risks as a result of participating in the research project. Similarly we foresee no direct financial or legal risks as a result of participating in the research study. Clients may be involved with the criminal justice system, but that involvement is overseen by other entities and is not a part of the research project. If we find the participant is intoxicated at baseline or follow-up assessment they will be voluntarily retained at the site until they are legally sober. There are three potential areas of risk: (1) perceived coercion to participate in the study; (2) a risk of some psychological harm in carrying out treatment studies. Participants may find answering some of the questions causes discomfort, or that participating in treatment with a family member contributes to relationship distress; (3) potential breaches of confidentiality. Methods for managing these potential risks are outlined below.

Perceived coercion: We are working with clients who may have been convicted of DWI or otherwise are involved in the criminal justice system. However, the treatment they receive as part of this research study has no bearing on the requirements they need to fulfill obligations with the court. We will make it clear both verbally and in the Informed Consent form that participation in the treatment study will neither help nor hinder their standing with the courts. Further, only clients who have voluntarily admitted themselves (i.e., are not court-mandated) to treatment at TLH will be eligible for study participation.

Although participants in this study are not prisoners, they may be involved in the criminal justice system insofar as they have been convicted for an alcohol related offense. We will make it very plain that data collected as part of the research study will not be available to the courts and will have no bearing on their status with the courts. Because they are not prisoners they will not require special protections, but we still need to be mindful that simply being involved in the criminal justice system makes them more vulnerable than a group not involved in the criminal justice system.

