More generally, it is possible that patients may believe they should participate to maintain good standing with their treatment providers. The recruitment and informed consent processes will clearly state that participation in the study intervention or subsequent withdrawal will have no impact whatsoever on their course of treatment.

Potential psychological harm: There is always a risk of some psychological harm in carrying out treatment studies. First, some of the questions in the assessment instruments may cause discomfort in some people. We have administered these measures in previous research studies and have found that they cause minimal distress to most people. If time needs to be taken so the person can compose themselves the interviewers will allow them to do so. In the unlikely case that a question causes severe discomfort, senior clinical staff from TLH will be called in and the PI will be contacted by phone. All data collection will be completed by experienced interviewers from the CASAA Program Evaluation Services (PES), who have had training in how to deal with crises, such as giving respite time, calling a clinician, and when to call a crisis center. The second potential source of psychological harm is that the provision of family-involved treatment could increase conflict in the family. Families in which there is domestic violence will be screened out of the study, so the risk of actual physical violence will be decreased substantially. One of the most consistent findings for family-involved treatment for alcohol and other substance use disorders is an increase in couples or family satisfaction and a decrease in domestic violence, and the B-FIT treatment protocol is designed to teach better communication skills,

thus mitigating the chance of increased conflict. The therapy will be given by licensed and trained counselors who have experience working with people with substance use disorders, and they will receive formal training and on-going supervision in the B-FIT protocol. If a participant (patient or CFM) finds some of the issues difficult the counselor can help them work through those issues. Furthermore, the research staff includes licensed clinical psychologists who will provide backup consultation to the therapists.

Potential breaches of confidentiality: The third risk is the possibility of a breach of confidentiality. Several steps will be taken to minimize the risk of breaches of confidentiality:

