There is also a risk that patients or family members could be under the influence of alcohol or drugs and therefore at diminished decision-making capacity. It will be at the discretion of staff obtaining consent or collecting assessments to use a breathalyzer on a patient or family member showing signs of intoxication; as there is no reliable method for assessing acute drug intoxication, staff will have the discretion to preclude participation based on visible impairment regardless of breathalyzer results. Clinicians conducting therapy sessions will use the same discretion. This information will be made clear in the informed consent forms. The informed consent forms will also include a short quiz to help ensure that patients and family members fully understand the nature of study participation (see appended).

II. Inclusion and Exclusion Criteria

Participants will include patients receiving services at TLH and a CFM who is willing to participate in the treatment and research. To be included, patients must: (a) have voluntarily initiated treatment (not been court-mandated) and had at least one alcohol treatment session in the last 30 days; (b) meet DSM-5 criteria for an AUD; (c) have an adult family member who is willing to participate; (d) be at least 18 years of age; (e) able to speak and read English at a 6th grade level; (f) not show current psychotic symptoms; and (g) not meet criteria for a severe non-alcohol substance use disorder. Family members will be included if they: (a) are at least 18 years of age; (b) able to speak and read English at a 6th grade level; (c) have in-person and/or telephone/text/email contact with the patient at least 4 days per week; (d) are rated as "important" by the patient on the Important People Interview (Longabaugh & Zwiak, 1999); (e) are willing to participate in treatment by coming to family visiting hours; (f) are not seeking treatment for an alcohol or drug problem of their own; (g) do not show current psychotic symptoms; and (h) do not meet screening criteria for a current alcohol or other drug problem. Patients and family members also will be excluded from the clinical trial if either partner reports domestic violence in the past 12 months serious enough to warrant medical attention, or if either reports concerns about participating in treatment with the patient/family member.

III. Participant Enrollment

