(4) We will create separate Excel spreadsheet logs of screens for patients and CFMs. All screens will be logged into the spreadsheets with a yes/no for whether the individual meets each inclusion/exclusion criterion. Individuals will be identified on the spreadsheet by screen participant number. The screening spreadsheet will not contain names or contact information. Screens for ineligible individuals will be filed in a locked file cabinet in a locked room without names or other identifying information on the forms. If both the patient and CFM meet initial eligibility criteria and are interested in the study they will be assigned a study number, a file will be created for them, and their screens will be filed in their study file. A second spreadsheet with study ID numbers and participant names for individuals who meet initial screening criteria and are interested in the study will include a field for screen participant number. Because the screens and spreadsheet for ineligible potential participants will never have identifying information we plan to retain these data on the same schedule as other data (five years post publication). The data from the screens will be used to report the number of individuals screened, and reasons for ineligibility.

V. Participant Withdrawal

Consent forms (see appended) will clearly state that participants may withdraw from the study intervention at any time for any reason and that this will not affect their course of treatment or standing in the criminal justice system (if applicable). The research team will withdraw participants in the event that evidence of domestic violence or severe psychopathology is detected after the initial screening, as these factors could interfere with treatment. Participants who withdraw from treatment will continue to be tracked for follow-up data collection. Participants who withdraw completely from the study will no longer be tracked, although their data will be retained unless they request otherwise.

PRIOR APPROVALS/REVIEWED AT OTHER IRBS

This project will not be reviewed at another IRB.

REFERENCES

Anton, R. F., O'Malley, S. S., Ciraulo, D. A., Cisler, R. A., Couper, D....Zweben, A. (2006). Combined pharmacotherapies and behavioral interventions for alcohol dependence: The COMBINE study: A randomized controlled trial. *JAMA*, 295, 2003-217.

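### Physical violence is treated as a residual risk of family-involved treatment, but its only scheduled measure is at screening, so the trial cannot describe it fairly by arm

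*Combined protocol and SAP*

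**What the plan says.** The section on risks opens with a general statement: "We foresee no physical risks as a result of participating in the research project". Further down, under Potential psychological harm, it says: "The second potential source of psychological harm is that the provision of family-involved treatment could increase conflict in the family". The next sentence says that families with domestic violence are screened out, "so the risk of actual physical violence will be decreased substantially". That describes a risk made smaller, not one removed.

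The inclusion and exclusion criteria set a narrower rule. Apart from concerns about taking part, they exclude a dyad only for "domestic violence in the past 12 months serious enough to warrant medical attention".

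Table 1 lists the "Partner Violence Screen" twice, once in the patient eligibility block and once in the CFM eligibility block, as a 2-minute interview. The text on initial screening and the section on recruitment and screening procedures place it at the same point.

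Under Participant Withdrawal, the team withdraws participants if "evidence of domestic violence or severe psychopathology is detected after the initial screening". No instrument or schedule for that detection is given.

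Family conflict is handled differently. Under Aim 2a, the Conflict subscale of the Family Environment Scale is a named outcome. The 4-month reports of patient and CFM are each compared between arms, with baseline values as covariates, two-tailed at 0.025.

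**The concern.** The plan allows that some risk of violence remains after screening and attaches a consequence to finding it, yet never schedules the question again. If few or no cases come to light, the reader cannot tell whether few occurred or few were heard about.

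The routes that remain are also unequal between arms. B-FIT dyads sit together with a therapist three times, and those sessions are recorded and reviewed. TAU families do not usually take part in treatment. The same underlying rate of violence could therefore produce more known cases in B-FIT, and a count of withdrawals or adverse events would mislead in that direction. A developmental trial that is meant to inform a larger one should at least be able to say what was reported in each arm when everyone was asked.

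**Working it through.** The documents state no figure on this point, so there is none to reproduce. The check is a reading of the schedule, followed by a calculation of what a repeated measure could and could not deliver.

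**1. Where violence is asked about**

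| Place | Content | Time | Violence instrument? |
|---|---|---|---|
| Table 1, eligibility blocks; Initial screening; Recruitment and Screening Procedures | Partner Violence Screen, patient and CFM | Screening | Yes |
| Within treatment data collection | Drinking, CFM distress, use of B-FIT interventions, satisfaction | Sessions | No |
| Table 1, remaining rows | Substance use, consequences, CFM mood, mediators, satisfaction | Baseline to 4 months | None named |
| Participant Withdrawal | Withdrawal on detection | Any time | No source named |
| Unanticipated Problems | Form for unanticipated adverse events | Any time | No violence category, no comparison by arm |

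Table 1 is broken in the available text, but each Partner Violence Screen row carries a single mark, and the prose agrees that it belongs to screening. A revised conflict tactics scale is in the reference list but appears in neither Table 1 nor the procedures.

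**2. What the conflict analysis covers.** Inputs are 34 B-FIT and 17 TAU participants after 15% attrition (Statistical power section; 40 × 0.85 = 34 and 20 × 0.85 = 17), two-sided alpha 0.025 and 80% power. The correlation r between baseline and 4 months is my assumption.

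Detectable difference = (2.241 + 0.842) × √(1 − r²) × √(1/34 + 1/17)

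- r = 0: 0.92 SD
- r = 0.5: 0.79 SD
- r = 0.7: 0.65 SD

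This is imprecise, but it is a randomised comparison that can move in either direction. The gap is therefore confined to physical violence.

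**3. What a 4-month violence item would add.** If no dyad reports violence, the exact one-sided 95% upper bound is 1 − 0.05^(1/n):

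- B-FIT, n = 34: 8.4%
- TAU, n = 17: 16.2%

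The documents give no violence rate, so the rates below are assumed. Power at two-sided 0.05 with 17 v 34 dyads:

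| TAU v B-FIT | Normal approximation | Fisher's exact test |
|---|---|---|
| 5% v 15% | 0.14 | 0.06 |
| 10% v 20% | 0.12 | 0.08 |
| 10% v 30% | 0.33 | 0.30 |

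The item supports description by arm and not a reliable test.

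**4. Cost.** 60 dyads × 2 people × 2 minutes = 240 minutes, or 4 hours.

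**The case against.** The strongest reply is that the risk the protocol actually names is conflict, and conflict is measured in both members of the dyad and tested two-tailed by arm. That is correct. A reader might infer that the trial cannot show whether B-FIT made family conflict better or worse. The Aim 2a analysis rules that reading out.

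A second reply is that physical violence is not among the three listed risk areas and is not an Aim 2a outcome. The remark that family-involved treatment reduces domestic violence summarises earlier research and is not a hypothesis of this trial. This also stands, so failing to confirm that remark is no fault of the plan. It does not answer the narrower point, because the protocol itself treats violence as reduced by screening, and the withdrawal rule presupposes that it may be found later.

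Third, some information will arrive anyway through CFM distress forms, recorded sessions, supervision and adverse event reports. It would be too strong to say that nothing could be learned. The item content of the follow-up consequence inventories also cannot be checked, because the appended assessments are not available. But these routes are passive and favour detection in B-FIT.

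Fourth, a reader might argue from "The average residential stay is 18-21 days" that most of the 4 months falls after discharge and that the danger therefore lies there. The protocol does not say so. Elapsed time is not risk, and outpatient recruitment is also planned.

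Finally, it is tempting to expect that a follow-up item would show whether B-FIT raised or lowered violence. With 34 and 17 dyads it would not.

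**Conclusion.** The point holds for physical violence only. No violence instrument is scheduled after screening, the remaining routes of detection are passive and probably unequal, and the trial will have no fair description of violence by arm. No efficacy result is affected. This is an inexpensive improvement to safety description, not a flaw that undermines the trial.

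The size is modest. As planned there is no bound on the violence rate in either arm. With the item added and zero events, the upper bounds would be about 8.4% and 16.2%. These figures rest on the planned 34 and 17 dyads with complete answers. That detection would favour B-FIT is a judgement from the number of joint sessions, not a measured quantity.

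Two pairs of statements must be reconciled. The first is the absence of any foreseen physical risk against a violence risk that screening reduces. The second is the claim that families with domestic violence are screened out against an exclusion limited to recent violence serious enough to need medical attention.

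**What to change.** - In Table 1, add the physical-violence items of the existing Partner Violence Screen at the 4-month follow-up, for patient and CFM, in both arms. Interview the two separately, as is already done at baseline.
- Word the items to refer to the enrolled patient and CFM, since the CFM may be a parent or other relative, and set the recall period to the time since baseline. If the exclusion criterion's 12-month window were kept, a 4-month visit would also pick up 8 months before baseline (12 − 4).
- Report counts by arm and informant with exact intervals, as a descriptive safety outcome without a hypothesis test.
- In the withdrawal section, name the source from which later violence is to be detected, and say whether dyads withdrawn by the team remain in follow-up, because losing them would distort the counts.
- Reconcile the two pairs of statements on physical risk and on the violence exclusion.

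The cost is about 2 minutes per person at an existing visit (about 4 hours in all for 60 dyads) and an amendment. The real addition is a stated procedure for handling positive answers: the confidentiality section describes the emergency procedure only for suicidal ideation, so it should not be assumed to cover disclosed violence.
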